11.0 Data Management

Regarding data management and storage, all data will be collected using coded questionnaires and case report forms. Only participants' study identification codes will be inputted in computer-based databases. All participants will receive a participant identification number at the time of consent, which will be linked to their data in a master list with participant names and contact information and kept by the PI/study coordinator electronically in password-protected network storage (MUSC Box). Consent forms will be kept either in a locked drawer in the PI's office or electronically in password-protected network storage. Hard copies of the case report forms will also be kept in a locked drawer in the PI's office. Assessments will be administered via in-person or app-based communication, or via REDCap data entry, which will be programmed to check data at the time of entry to ensure that entered values are within the specified range and that items are not inappropriately skipped. The data will be imported directly into a password-protected statistical software data file (e.g., SPSS) stored on MUSC's secure server. The MUSC server has a 1TB hard disk capacity, 4GB of RAM, dual 3000MHz processors, and 100% drive redundancy to safeguard all data and minimize disruptions in the event of hardware failure. The server is protected by the MUSC network, and a secured log-in is required from all users. In addition to these precautions, all personnel will have earned at least a bachelor's degree and have experience in conducting research. All research personnel collecting and handling data will have completed a Human Subjects Research Training course offered through the MUSC Compliance Division and will be supervised by [name] to ensure strict compliance with the DSMP. Only IRB-approved study personnel ([name] and study team) will have access to data. No data will be released to other agencies unless participants consent to release.

The following data will be collected and analyzed: Feasibility processes include recruitment and drop-out proportions, protocol adherence and patient and provider satisfaction will be assessed at 1 month. We will use 95% CIs for proportions to estimate dichotomous outcomes (proportions of subjects who agree to participate out of the number who are initially approached), the proportion who are adherent to protocol (e.g. opening messages, bi-monthly provider reports), the proportion who report satisfaction with intervention, and the proportion who exit the study prematurely (drop out). In addition, frequency distributions will be developed describing reasons for provider and patient protocol non-adherence, drop out and problems encountered such as technology glitches, etc. For the continuous feasibility measures (e.g., number of technology help requests, provider and patient satisfaction scores from patient surveys and end-of-study interview), frequency distributions and the median and mean responses (with 95% confidence intervals) will be obtained. For relevant categorical feasibility measures, chi-square tests will be used to compare the 2 groups. Pooled *t*-test (or Wilcoxon rank sum tests) will be used to compare the groups for continuous feasibility measures. We will also compare demographic and clinical characteristics for those who were eligible for study versus those who were not eligible and for those who adhered to the study protocol (study completers) versus those who did not adhere (non-adherers and drop-outs).

Quantitative analyses: In preparation for a subsequent adequately powered RCT, the planned primary clinical outcomes will be investigated. Those include variables such as time to healing, time to treatment change, and number of clinical encounters. Determination whether a wound has healed or become infected will be made at routine intervals based on clinical judgement from baseline through the day of burn healing and a final assessment 1 month after it was determined as 'healed'. Analyses for these measures

focus on variability and precision of estimates rather than magnitude of effect sizes. 95% confidence intervals (CIs) of the difference in mean days to healing (or treatment change/infection) between interventions will be obtained. In addition, survival distributions and their 95% CIs will be obtained for each intervention arm using the Kaplan-Meier product limit method. Further, 95% CIs for hazard ratios will be obtained using Cox proportional hazards regression to model time to healing (treatment change) as a function of the intervention. In the future RCT, generalized linear mixed models (GLMM) will be used to obtain estimates of the variances of the clinical outcomes and the covariance structure of longitudinal measures as critical input information for determination of sample size (and hence adequate power) [82, 83]. Frequency distributions of AEs and SAEs will be used to characterize each intervention group. Analyses of caregiver data will include pre- and post-treatment group differences (TOBI vs. FTF) to understand factors related to caregiver well-being and adjustment following mHealth burn treatment and possible predictors of outcomes. These analyses may include mixed design repeated measures analyses of variance (ANOVAs) and regressions.

When the study is concluded, after 6 years all records related to the study will be destroyed. Furthermore, all staff will sign confidentiality agreements, and training sessions will emphasize the critical importance of confidentiality. The likelihood that these methods will effectively protect the confidentiality of participants is considered to be extremely high. Based on our experience with previous research projects, it is believed that these procedures will be effective in protecting confidentiality of subjects and minimizing any potential risk from participation.

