The current ongoing Phase I study (**Pro00092341**) aims to refine TOBI, using qualitative research directed at stakeholder feedback, including caregivers and expert burn providers, to make the app/portal more "user-friendly." The ongoing project involves semi-structured interviews, assessment of satisfaction/usability and caregiver well-being and adjustment, and subsequent consumer-driven adjustments to the app to ensure high acceptability and usability. These adjustments will focus on improving patient adherence as well as provider barriers to implementation in preparation for a feasibility RCT.

Following optimization of TOBI app/portal, **the proposed feasibility RCT of burn care utilizing TOBI will be conducted.** The proposed study will recruit 64 patient/caregiver dyads from our pediatric burn center who are under outpatient medical treatment for a partial thickness burn and will randomly assign them to outpatient burn therapy enhanced with TOBI (TOBI) (n=32) vs. standard outpatient face-to-face (FTF) (n=32) therapy.

The **objective** of the proposed study is to assess the feasibility of the TOBI intervention and RCT research protocol in preparation for a subsequent large-scale multi-center RCT comparing outpatient burn care enhanced with TOBI vs. standard care. We will obtain preliminary indicators of effectiveness of the intervention rather than testing hypotheses. Clinical outcomes (burn healing, infection, change in therapy, adherence, and unexpected return to clinic/emergency room) will be assessed during baseline and at clinically determined intervals with (TOBI) or every clinic visit (FTF). We will also assess caregiver self-efficacy, stress, and well-being using psychometrically validated measures to understand whether these factors play a role in service utilization and outcomes. Many factors affect the successful implementation of an intervention that changes clinical practice, like TOBI [69]. The feasibility study is not sufficiently powered to make firm conclusions about TOBI's effectiveness, but will critically assist in identifying barriers to recruitment, retention, and procedures essential toward successfully conducting a large-scale, multicenter RCT. This is consistent with expert recommendations to test the feasibility of conducting an RCT while avoiding hypothesis-testing and yielding data to "debug" the methodology and assess optimal strategies for executing the RCT [69-72].

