10.0 Study Design / Methods

The RCT will include 64 patient/caregiver dyads recruited from the MUSC outpatient burn clinic, hospital floor, or pediatric emergency room, randomized to burn care enhanced with TOBI (n=32) or FTF standard care (n=32). After obtaining informed consent, the research staff will create a new patient record in the REDCap database and assist (if needed) the caregiver in completing the initial questionnaire battery using the REDCap survey. The baseline questionnaires, completed by the caregiver, will include the demographics form, measures about attitudes toward telemedicine, perception of healthcare access, affect, depression, anxiety, self-efficacy, and peritraumatic distress (see measures attached). All PHI will be protected by a study ID to promote confidentiality. The family will receive a ClinCard at the beginning of the study which works like a bank debit card and can be used to purchase goods or services everywhere Debit MasterCard is accepted. Each time they receive payment for participation in this study, the money will be added to the card. Families will receive \$20 for completion of baseline assessment.

At the completion of questionnaires, caregivers will be randomly assigned to treatment conditions. Stratified permuted block randomization will be used to assign patients to either the burn care enhanced with TOBI or FTF care only (32 dyads per arm). Assignment will be stratified by provider to ensure balanced enrollment across the treatment arms regardless of numbers enrolled per provider. To minimize the likelihood that the blind will be broken, i.e. the next treatment assignment can be guessed, the block size will be varied.

Chart review will be conducted within approximately 72 hours of enrollment and data will be recorded in a chart review checklist and subsequently transferred into the database (e.g., burn mechanism, % TBSA, burn location, burn depth, date of burn injury, time to medical treatment, type of first clinical encounter [burn outpatient vs. emergency department vs. hospital discharge], and type of dressing).

Patients randomized to FTF will undergo standard burn care including a return follow-up in the burn clinic on a routine basis as prescribed by the clinical burn team (e.g., at least once per week) until the burn has healed. Healing is defined as greater than 95% epithelialization of the burn wound. This will be determined by a clinician.

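### The plan says it avoids hypothesis testing, yet its only between-arm analysis of feasibility measures is a low-powered significance test, with no interval for the difference

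*Combined protocol and SAP*

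**What the plan says.** Section 1.0 states the aim for clinical effect: "We will obtain preliminary indicators of effectiveness of the intervention rather than testing hypotheses". It then describes the design as "consistent with expert recommendations to test the feasibility of conducting an RCT while avoiding hypothesis-testing". The second statement is the one that matters here, because it concerns the feasibility of running the trial and not only its effectiveness. Section 6.0 adds that the sample size was chosen pragmatically, without a formal power calculation. Section 10.0 gives the allocation: dyads are "randomized to burn care enhanced with TOBI (n=32) or FTF standard care (n=32").

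Section 4.0 makes the feasibility outcomes the primary endpoints. For these, Section 11.0 starts with estimation: "We will use 95% CIs for proportions to estimate dichotomous outcomes". It lists agreement to participate, protocol adherence, satisfaction and dropout, and adds means and medians with 95% intervals for continuous measures. It then turns to the arms. For those categorical measures that are relevant, "chi-square tests will be used to compare the 2 groups". For continuous measures it names a pooled t-test ("or Wilcoxon rank sum tests) will be used to compare the groups for continuous feasibility measures").

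For the clinical outcomes, Section 11.0 says the analyses "focus on variability and precision of estimates rather than magnitude of effect sizes". There it plans 95% intervals for the difference in mean days to healing and for hazard ratios.

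**The concern.** The two sections point in different directions. Section 1.0 sets hypothesis testing aside, yet Section 11.0 makes a significance test the only stated between-arm analysis of the feasibility measures. The secondary clinical outcomes get estimated contrasts with intervals, while the primary feasibility endpoints get p-values. No significance level, multiplicity rule or reading of those p-values is given.

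What is at stake is interpretation. Section 4.0 wants to know from which condition patients dropped out, and Section 1.0 wants barriers to retention identified for the multicenter trial. A non-significant p-value for dropout or adherence could easily be reported as no difference between arms, when the data remain compatible with a gap large enough to matter for planning that trial.

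**Working it through.** **Inputs.** From the documents: 32 dyads per arm (Section 10.0) and an attrition benchmark of 20% (Section 4.0), the only target rate given for a primary feasibility endpoint. Assumed: two-sided alpha of 0.05, and every comparison rate other than 20%. The plan states no power or detectable difference, so there is no figure of its own to reproduce.

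**Which measures are affected.** Section 11.0 limits the chi-square test to relevant measures.
- Recruitment: randomization follows enrollment (Section 8.0), so there are no arms to compare.
- Treatment fidelity: defined for TOBI (Section 4.0).
- AEs, SAEs and technology glitches: described by frequency distributions (Section 11.0).
- Left for between-arm testing: mainly dropout, protocol adherence, satisfaction and, as a continuous measure, help requests.

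**Power of the chi-square test.** With p̄ the mean of the two rates and n = 32, the normal approximation is

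power ≈ Φ{ [ |p1 − p2| − 1.96·√(2p̄(1 − p̄)/n) ] / √([p1(1 − p1) + p2(1 − p2)]/n) }.

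- 20% vs 10%: (0.10 − 1.96 × 0.0893)/0.0884 = −0.85, power 0.20. Exact enumeration of all tables (Pearson, uncorrected): 0.20.
- 20% vs 40%: (0.20 − 1.96 × 0.1146)/0.1118 = −0.22, power 0.41. Exact: 0.42.
- If 20% attrition leaves 32 × 0.8 ≈ 26 per arm for measures taken at 1 month, the exact figures fall to 0.18 and 0.37.
- Starting from 20%, 80% power at 32 per arm needs about 54% in the other arm. For 20% vs 10%, 80% power needs 199 per arm.

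**Power for continuous measures.** 80% power needs a standardized difference of (1.96 + 0.84) × √(2/32) = 0.70. At 0.5, power is 0.52.

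**A worked example.** Take dropout of 9/32 vs 4/32. Overall this is 13/64 = 20.3%, in line with the benchmark.
- Chi-square = 64 × (9 × 28 − 4 × 23)² / (32 × 32 × 13 × 51) = 2.41, p = 0.12.
- Wilson 95% limits: 0.281 (0.156 to 0.454) and 0.125 (0.050 to 0.281).
- Newcombe lower limit: 0.156 − √[(0.281 − 0.156)² + (0.281 − 0.125)²] = −0.04.
- Newcombe upper limit: 0.156 + √[(0.454 − 0.281)² + (0.125 − 0.050)²] = +0.34.

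The test says not significant. The interval says anything from 4 points in one direction to 34 in the other.

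**Are the tests valid?** The exact type I error of the uncorrected chi-square at 32 per arm is 0.004 at a 2% rate, 0.032 at 5%, 0.056 at 10%, 0.051 at 20% and at most 0.060 (at 50%). The expected count is 32p, which is 6.4 at the 20% benchmark; there, an observed table has an expected count below 5 in 15% of trials. That share rises to 50% at a 15% rate and 90% at 10%, but the error rate still stays near or under nominal. The pooled t-test, simulated with skewed data at 32 per arm (20,000 runs), kept 0.049 (Poisson, mean 0.5), 0.048 (negative binomial, mean 1) and 0.039 (lognormal).

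**The case against.** The plan is not built on p-values. Estimation is the first analysis named in Section 11.0, with 95% intervals for each proportion and for means and medians. Section 1.0 says the study is not powered for firm conclusions, and no progression criterion depends on a test result. One could also read the disclaimer as covering effectiveness only, since one of its two sentences concerns effectiveness, and the sentence on precision in Section 11.0 concerns the clinical outcomes.

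Much of this stands, and it keeps the point modest. It does not remove it. The other sentence in Section 1.0 ties avoidance of hypothesis testing to the feasibility of conducting the trial. Intervals for single proportions or means do not give an interval for the difference between arms.

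A reader might go further and infer that the tests are invalid at this sample size because event counts will be sparse and no exact test is named as a fallback. The documents do not support that. At the plan's own 20% benchmark, small expected counts are uncommon; the chi-square error rate never exceeds about 6%; and Wilcoxon is already offered beside the t-test. The chi-square approximation is doubtful only for rare outcomes, and there it tends to be conservative. Moving to Fisher's test would not help: for 20% vs 10% its power is 0.11. Nor can the point be extended to all primary feasibility endpoints, since several are never compared between arms.

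**Conclusion.** The point holds in a limited form. The stated approach and the planned between-arm analysis contradict each other, and the tests can detect only very large differences: from 20%, roughly 34 points (54% vs 20%) for 80% power. A non-significant result would therefore carry little information about dropout, adherence or satisfaction. The missing item is an interval for the between-arm difference in feasibility measures.

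The power figures assume a two-sided 0.05 level and illustrative comparison rates; only the 20% comes from the plan. The dropout example is hypothetical. Severity is modest: the risk is misreading, and no decision rests on the p-values.

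**What to change.** In Section 11.0, replace the between-arm tests of feasibility measures as follows.

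- Categorical measures: the difference in proportions, TOBI minus FTF, with a score-based 95% interval such as Newcombe's.
- Continuous measures: the difference in means, or the Hodges-Lehmann shift where the data are skewed, with a 95% interval.
- P-values: state that none are reported for these measures, or that any reported are descriptive and will not be read as showing equivalence.
- Scope: list the measures to be compared between arms.

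The single-arm and overall intervals already planned can stay as they are. The cost is a few sentences of wording, with no new data or participants. What is given up is a formal test of feasibility differences, which the stated approach does not call for.

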3.0 Intervention to be studied

Telemedicine, in various forms, is feasible in burn care [24-26] and facilitates the delivery of care to patients with burn injuries of all sizes [27]. Mobile health (mHealth) technology, offers a promising approach to address barriers [28], but has never been used to provide expert burn care in the home. Smartphone app-based burn injury care exists in practice, although rigorous scientific validation has not been achieved. The MUSC pediatric burn team has partnered with TACHL (Technology Applications Center for Healthy Lifestyles) to provide pediatric patients and their families with state-of-the-art burn care at home using a novel mobile health technology, called the Telemedicine Optimized Burn Intervention (TOBI). TOBI is a smartphone application synced with a portal used by providers, as an adjunct to standard therapy. This burn app provides education through frequently asked questions, instructional burn dressing change videos, and direct communication between patient and burn expert through store-and-forward pictures and videoconferencing.

The ongoing Phase I study (**Pro00092341**) builds upon our proof-of-concept study using a smartphone app to provide expert burn care to children in the home. Feedback from pediatric burn patients, parents, and their health care providers guided initial development and pilot testing of TOBI, which connects clinicians and caregivers through text-messaging, wound image transfer, and video-conferencing. We conducted an open trial (n=32) using TOBI and found high parental and provider acceptability and usability. Comparisons against a historical comparison group suggested quicker time to detect healing, fewer in-person clinical encounters, and greater adherence to treatment among families using TOBI vs. standard care [4]. Rigorous scientific study is needed to validate this novel clinical care pathway as mHealth technology shifts the fundamental structure of the provider-patient relationship. The ongoing Phase I study will culminate with evidence-based optimization of TOBI based on stakeholder feedback prior to the proposed RCT.

Innovation

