Patients randomized to burn care enhanced with TOBI will be given instructions and will be aided in downloading TOBI onto their smartphones. Patients with TOBI will be able to use standard FTF care as well. They will demonstrate an ability to use the various components of TOBI during initial visit and enrollment and will be explained how to contact the burn team through the hospital paging operator if TOBI is unavailable. Similar to the FTF group, they will be given oral and written instructions about standard burn care with routine clinical care delivered via TOBI, including a plan to interface with the burn clinicians (text messaging, videoconferencing, or image transfer) on a routine basis. TOBI patients will be scheduled for weekly videoconferencing encounters through the app until the burn has healed. Patients will be asked to come in-person if would complications are noted by a clinician (e.g., non-healing, infection). If technological problems with TOBI are encountered (e.g., video stops working), providers may switch to another secure telehealth platform to provide the necessary care and will document technology issues appropriately, as part of feasibility assessment.

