Clinical data will be collected on case report forms by the clinical care team (e.g., burn nurse, physician) and entered into the REDCap database in a coded manner by a research assistant (who is blind to the treatment condition to reduce bias during data entry) at clinically determined intervals per routine care based on clinical judgment with TOBI or FTF (see table below). The duration and number of clinical encounters for both conditions will be guided by best clinical practice and each patient's needs. On average, most burns that meet the study eligibility criteria require 2-5 visits and heal within 2-4 weeks. Case report forms will be generated with study ID only, with no identifiable PHI in order to protect patient's privacy. Data collected at intervals will include adherence to prescribed wound care, change in therapy, wound complications, day of healing, pain scores, sleep problems, unexpected return to clinic or emergency room (see Clinical Case Report Form attached). App metrics, such as number of videoconferences, number of text-messages, number of photos, and scripted messages by burn professional will be recorded by the app software and exported at the end of the study. Images of wounds will not be stored for the purposes of this study. They may be uploaded by clinical care team members into the patient's medical record as part of standard care procedures (outside of the study). Adherence to therapy will be defined as parent/patient performance of prescribed wound care through the end of treatment. Overall compliance with therapy is defined as documentation of healed burn through TOBI or FTF. Clinical data collection will continue until 1 month after the burn is diagnosed as healed by a burn physician in either condition (FTF or TOBI).

At 1-month, caregivers will be asked to complete the post-treatment questionnaires by phone or virtually using the REDCap survey, using a public link and study ID to identify their survey. This assessment will include measures about attitudes toward telemedicine, perception of healthcare access, affect, depression, anxiety, perceived stress, posttraumatic growth, treatment satisfaction, and app feasibility (TOBI only group) (see measures attached). Collected data will be entered into REDCap by the study staff. Overall, participation rate will be recorded. Families will receive \$30 following completion of post-treatment assessment.

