- Patients in both groups will receive an initial FTF visit either in the burn clinic, hospital, or emergency department. In routine outpatient burn care, the primary risks of burn treatment include burn wound infection, non-healing, and pain. Burn wound infection is the highest risk complication, but, fortunately, is very uncommon in pediatric burn wounds. In adults, burn wound infection approaches 5% in some studies. Data of the incidence of outpatient burn wound infection in children is incomplete, although anecdotal evidence from our practice suggests that outpatient burn wound infection is extremely uncommon. In our pilot series of 32 patients treated with TOBI, none had burn wound infection. Burn wound infection would be normally assessed on visual inspection of the wound and a clinical history of fever. In order to mitigate the small, potential risk of burn infection that is misdiagnosed by using TOBI communication, each daily digital interaction (e.g., video-conferencing, or image-transfer) will be prompted with a dialogue box asking the caregiver if the patient has had a fever in the last 24 hours. This will enhance detection of fever in a burn wound infection patient. In terms of other short-term complications measured, including non-healing or pain, if there is a suspicion that these two clinical outcome measures were inadequately treated by TOBI, the patient will be requested to make a FTF visit.
- [name] is a licensed surgeon in South Carolina and has over 12 years of experience assessing and treating patients with burn injury. He will closely supervise all study staff, and will hold weekly meetings with the team during the initial recruitment of patients. He and his partners will provide burn care using both modalities, as is their current clinical practice. All burn surgeons and therapists at MUSC will undergo training in the study procedures. All staff will have cell phone numbers where Drs. [name] and [name] will be available. [name] will coordinate his schedule with staff to ensure that he is available during any staff-patient interactions. In the rare instance where he cannot be reached, [name] will serve as the clinical backup and will follow these protocols and standards.

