15.0 Potential Benefits to Subjects or Others

The potential benefit to participants is that the services they receive may be more helpful or convenient than other available services, although this cannot be guaranteed. For example, if the patient/caregiver dyad is in the group that proves to be better than the other group in this study, the dyad may benefit from this study. Youth and their caregivers receiving services using the TOBI app, will have access to a resource that has potential to improve clinical outcomes, including burn healing time, faster treatment of burn wound complications, decrease travel time, and promote greater adherence to burn wound therapy.

It is hoped that the information gained from this study will help in the treatment of future patients with burn injury. Completion of this study may improve the quality of and access to expert burn care for pediatric surgical patients and their families and may relieve the burden on burn providers by allowing them to remotely direct treatment in the patient's home. The proposed study is a feasibility RCT in MUSC's burn center done in preparation for a subsequent large-scale multi-site RCT. This study will provide valuable data toward understanding how mHealth resources can affect the delivery of healthcare and improve healthcare access and clinical outcomes while leveraging a scalable, sustainable technology platform. It also will set the stage to address key questions around the implementation, dissemination, and sustainability of technology-facilitated treatment approaches in clinical practice settings. The proposed approach is highly sustainable due to low costs of disseminating these resources, and therefore has the ability to have wide reach and impact in the general population.

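### If healing is dated at the look that finds it, unequal looks between the arms shift mean days to healing by about half the difference in look interval; a dating rule and one sensitivity analysis would cover this

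*Combined protocol and SAP*

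**What the plan says.** Section 10.0 defines healing as more than 95% epithelialization, judged by a clinician. Section 11.0 says when that judgement is made: "Determination whether a wound has healed or become infected will be made at routine intervals based on clinical judgement from baseline". The case report form items are listed in section 10.0: "Data collected at intervals will include adherence to prescribed wound care, change in therapy, wound complications, day of healing, pain scores, sleep problems". The form itself is not in the text available for review, and no passage says whether the day of healing is the date of the look or an estimated earlier date.

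On how often the wound is seen, section 10.0 says of the app arm: "TOBI patients will be scheduled for weekly videoconferencing encounters through the app until the burn has healed". That arm also has routine messaging and image transfer, and may use the clinic. The face-to-face (FTF) arm returns as the burn team prescribes, with weekly given as an example of the minimum. For both arms, "The duration and number of clinical encounters for both conditions will be guided by best clinical practice and each patient's needs".

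Section 11.0 then plans a 95% CI for the difference in mean days to healing, Kaplan-Meier curves by arm and a Cox hazard ratio. It says these analyses are about variability and precision rather than effect size.

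Section 3.0 describes the pilot comparison with historical patients in terms of detection: it "suggested quicker time to detect healing, fewer in-person clinical encounters". Section 15.0 speaks of healing itself: the app "has potential to improve clinical outcomes, including burn healing time".

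**The concern.** A wound that heals between two looks is recorded as healed only at the second, unless someone back-dates it. The recorded time is then the true time plus a delay, and the delay grows with the gap between looks. Equal gaps in the two arms make the delays cancel in the comparison. If one arm is looked at more often, its healing is found sooner and the contrast moves in its favour with no true difference.

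This trial compares two ways of arranging contact with the burn team, so look frequency is something the intervention may itself change. A reader of the results could not then separate faster healing from earlier detection, and the plan uses both descriptions.

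**Working it through.** The documents give no SD, effect size or detection delay for healing, so there is no stated figure to reproduce.

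**Inputs**
- Scheduled looks: every 7 days in both arms (section 10.0). Unequal intervals of 5 and 3.5 days are assumptions.
- Healing time: median 14 days, since section 2.0 says the majority heal by then. Lognormal shape and SD 4.0 to 7.3 days are assumed.
- Patients: 32 per arm, or 26 per arm after the 20% attrition benchmark in section 4.0 (32 x 0.8 = 25.6).
- No true difference. Recorded date = first look at or after healing.

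**Mean days.** With looks every L days, unrelated in timing to healing, the delay is uniform on (0, L) with mean L/2. The spurious difference is (L1 - L2)/2.
- 7 v 7: (7 - 7)/2 = 0 days.
- 7 v 5: (7 - 5)/2 = 1.0 day. Simulated: 0.9 to 1.1.
- 7 v 3.5: (7 - 3.5)/2 = 1.75 days. Simulated: 1.7 to 1.8.

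Swapping the arms reverses the sign.

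**Scale.** Ignoring look error, the 95% CI half-width is t x SD x sqrt(2/n). With t = 2.0 and n = 32 this is 2.0 x 4 x 0.25 = 2.0 days for SD 4, and 2.0 x 7 x 0.25 = 3.5 days for SD 7. With look error simulated, it is 2.1 to 3.8 days at 32 per arm and 2.4 to 4.2 at 26. A 1-day shift is thus about a quarter to a half of the half-width at 32 per arm (1/3.8 = 0.26; 1/2.1 = 0.48). The CI for mean days wrongly excludes zero in 4-6% of simulated trials with equal weekly looks, 7-15% with 5 v 7, and 16-38% with 3.5 v 7.

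**Kaplan-Meier.** Without censoring, the area between the curves equals the difference in means, so on average the curves separate by the same number of days. The median need not. In a run with mean 14 days and SD 3, 5 or 7, the 3.5 v 7 median shift was 1.8 to 1.9 days when look days were spread across patients. It was 0 when all looks were counted from a common day zero, because day 14 falls on both grids.

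**Cox.** A hazard ratio has no unit of days, so the half-interval rule does not apply to it. In that run, with spread look days, the same 1.75-day shift gave TOBI:FTF hazard ratios of 1.69, 1.42 and 1.23 for SD 3, 5 and 7. For 5 v 7 days under the main inputs the range is 1.12 to 1.34 if TOBI is seen more, and 0.75 to 0.90 if FTF is.

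**Which intervals are plausible?** Section 10.0 says: "On average, most burns that meet the study eligibility criteria require 2-5 visits and heal within 2-4 weeks". Healing at 14 to 28 days means 14/7 = 2 to 28/7 = 4 weekly looks, but 14/3.5 = 4 to 28/3.5 = 8 looks at 3.5 days. The simulated share of patients with 2 to 5 looks is 92-99% for weekly, 85-98% for every 5 days and 60-80% for every 3.5 days. With a median of 18 days the last share falls to 33-46%. So 5 v 7 is compatible with the protocol's figures, and a whole arm at 3.5 days is a high case that fits them poorly.

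**Does using the interval help?** Midpoint dating (halfway between the last not-healed look and the first healed look) subtracts L/2 from each arm. In simulation it brings the mean difference within 0.1 day of zero, with the CI excluding zero in 4-6%. Cox on midpoint dates gives hazard ratios of 0.97 to 1.04, excluding 1 in 3-7%. An interval-censored lognormal model gives time ratios of 1.00 to 1.02, excluding 1 in 4-7%.

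**The case against.** The case against has four parts.

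- **The written schedules match.** Both arms are at least weekly, and equal looks give no bias. This stands, and is why the point is conditional. But weekly is a floor in one arm, the other has extra contact routes, and encounter numbers follow need, so equality is not assured.
- **The form may already deal with dating.** A separate day-of-healing item is compatible with back-dating, and accurate back-dating removes the problem. This also stands. The text gives no rule either way.
- **Little depends on it.** The trial avoids hypothesis testing, has no power calculation, and does not list time to healing in Aim 2 or section 4.0. That limits the consequence. Section 11.0 nevertheless names time to healing among the main clinical outcomes planned for the later trial, and still reports the between-arm intervals and hazard ratio.
- **Encounters are already counted.** The section 10.0 table collects total FTF and TOBI visits and app counts, and section 11.0 lists number of encounters as an outcome. So it would be wrong to say that look frequency goes unmeasured. What is missing is the link to the healing date.

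A reader might go further and infer daily looks in the TOBI arm from section 14.0, which says that "each daily digital interaction (e.g., video-conferencing, or image-transfer) will be prompted with a dialogue box". That would give (7 - 1)/2 = 3.0 days. The passage describes a fever question and does not say that healing is judged daily, so the documents do not support this reading. Nor do they support saying that the bias favours TOBI, since FTF children may be the ones seen more often, or that the pilot result was a detection artefact.

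**Conclusion.** The point holds as a possible bias with a cheap safeguard. It is not a demonstrated error in the plan. It needs two things that the documents leave open: that the recorded day is the look date, and that actual looks differ by arm. Given both, mean days and the Kaplan-Meier curve (on average) shift by about half the difference in look interval. That is about 1 day for 5 v 7 days, with 1.75 days as a high case. The hazard ratio moves in the same direction by an amount set by the spread of healing times, and a Kaplan-Meier median on a fixed look grid may not move at all. The direction cannot be predicted. These sizes rest on the assumed look intervals, SDs and lognormal shape. Under the main inputs the shift is smaller than the CI half-width, in a trial that disclaims effect-size inference.

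**What to change.** Keep the planned mean-days, Kaplan-Meier and Cox analyses, and add the following.

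1. State which contacts can date healing (video, clinic, photo or message between visits), and that the day of healing is the date of the look that finds it or, if not, how it is estimated.
2. Record the date and healed yes/no at each such contact in both arms.
3. Report the encounter counts already planned as looks per week until healing, by arm.
4. Add one sensitivity analysis using the interval from the last not-healed look to the first healed look. Either midpoint dating, which runs in SPSS (the package section 10.0 gives as an example), or an interval-censored model will do.
5. If looks differ between the arms, describe the contrast as time to detected healing.

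The cost is two or three sentences, one form line where it is lacking, and one extra analysis. The extra result depends somewhat on the midpoint or model assumption. It also assumes that look times do not depend on the wound. A photo sent because the wound looks healed breaks that assumption, and midpoint dating would then tend to place healing too early. How often any child is seen does not change.
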